3.3.1 Withdrawal, removal, and replacement of subjects

All subjects will be informed that they have the right to discontinue study drug or to withdraw from the study at any time, for any reason, without prejudice, and without having to justify their reasons or decisions. Additionally, the Investigator may discontinue a subject's study drug at any time if he/she considers that to be in the subject's best interest or if the Investigator determines that continuing study drug would result in a significant safety risk for the subject.

A discontinuation of study drug occurs when an enrolled subject ceases study drug, regardless of the circumstances, prior to completion of the study. However, every effort should be made to observe subjects who have been dosed until the scheduled end of the follow-up period, even if they prematurely discontinue study drug.

Withdrawal of consent for intervention should be distinguished from withdrawal of consent for follow-up visits and from withdrawal of consent for non-subject contact follow-up, eg, medical record checks. The site should document any case of withdrawal of consent.

If subjects no longer wish to take the IMP, they will be encouraged to remain in the study. The Investigators should discuss with them key visits to attend. The value of all their study data collected during their continued involvement will be emphasized as important to the public health value of the study. Subjects who withdraw from the study intervention should be explicitly asked about the contribution of possible AEs to their decision, and any AE information elicited must be documented. All study withdrawals should be recorded by the Investigator in the appropriate screens of the eCRF and in the subject's medical records. In the medical record, at least the date of the withdrawal and the reason should be documented.

In case of premature discontinuation of study drug, the Investigator should schedule an early termination visit to record AE data and to collect samples for laboratory evaluations. This visit should be documented in the appropriate eCRF. The Investigator will record the reason for the study drug discontinuation, provide or arrange for appropriate follow-up for such subjects, and document the course of the subject's condition. In addition, the Investigator will report the subject's study drug discontinuation or study withdrawal to the Sponsor immediately.

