7.2.2 Analysis populations

The **Intent-to-Treat (ITT) Population** will consist of all randomized subjects analyzed according to the treatment group allocated by randomization. The ITT Population will be the primary efficacy analysis population.

The **Safety Population** will consist of all subjects who receive at least one dose or partial of a dose of the IMP, analyzed according to the treatment actually received.

The **PK Population** will consist of all subjects who receive at least one dose of the IMP and have at least one post-dose PK sample to determine plasma concentrations of lademirsen (SAR339375).

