7.2.5 Efficacy analysis

Estimated GFR will be calculated using the CKD-EPI creatinine equation as described by (32). For French subjects, see [Section 10.5.3](#).

Annualized rate of change in eGFR during the placebo-controlled treatment period will be compared between lademirsen (SAR339375) and placebo using a linear mixed effect model. ATHENA Natural History Study (OBS16374) data will be used as prior information supplementing the placebo arm, using a Bayesian approach.

The model will include eGFR measurements from baseline to Week 48 as response variables, and it will include fix effects of treatment (lademirsen [SAR339375] or placebo), screening eGFR stratification factor, time, and treatment-by-time interaction. In addition, it will include random intercept and random slope for time to account for the between subject variability. Time will be treated as continuous variable based on actual eGFR assessment date relative to the randomization date.

A prior distribution for the slope of the placebo group was determined based on the annualized rate of change in eGFR observed in a subgroup of subjects from ATHENA Natural History Study, who are considered as rapid progressors meeting renal function criteria similar to I 05 in [Section 3.2.1](#). The prior distribution assumes a normal distribution for the slope of eGFR in the placebo group, with a mean of -10 and standard deviation of 2.22. Non-informative priors will be used for other parameters in the model. Efficacy of lademirsen (SAR339375) will be based on the posterior probability that the slope of the lademirsen (SAR339375) group is greater than the slope of the placebo group. A posterior probability of at least 95% will be considered significant.

The primary estimand will be the difference in mean slope of eGFR estimated from baseline to Week 48 in ITT population, regardless of whether or not subjects completed the study period of 48 weeks.

Change and percent change from baseline in eGFR at Week 24 and 48 will be analyzed using mixed effects model with repeated measures (MMRM), based on eGFR measurements up to Week 48.

The number and proportion of subjects who reach ESRD or initiation of hemodialysis or renal transplantation will be summarized by treatment group. The proportion will be estimated based on

total subjects in ITT population, as well as the Kaplan-Meier estimate taking consideration of lost to follow-up during the study.

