3 RESPECTIVELY ANALYSIS POPULATIONS

The following populations for analyses are defined:

Table 5 - Populations for analyses

Population	Description
Primary population	All randomized participants from Stage 1/Cohort 1 and Stage 2/Cohort 2 excluding subjects with low baseline eGFR (ie, baseline eGFR of 20 to 35 mL/min/1.73 m ²). Participants will be analyzed according to the intervention allocated by randomization.
Stage 2 Primary population	Primary population in Stage 2/Cohort 2 only.
Secondary population	All randomized participants from Stage 1/Cohort 1 and Stage 2/Cohort 2 including subjects with low baseline eGFR (ie, baseline eGFR of 20 to 35 mL/min/1.73 m ²). Participants will be analyzed according to the intervention allocated by randomization.
Stage 2 Secondary population	Secondary population in Stage 2/Cohort 2 only.
Safety population	All randomized participants from Stage 1/Cohort 1 and Stage 2/Cohort 2 who took at least 1 dose of study intervention. Participants will be analyzed according to the study intervention they actually received.
PK population	All treated participants from Stage 1/Cohort 1 and Stage 2/Cohort 2 who received at least one dose of the lademirsen and had at least one post doses PK sample for determination of lademirsen concentrations.
ADA population	All randomized and treated participants (safety population) who had at least one post-baseline ADA sample from Stage 1/Cohort 1 and Stage 2/Cohort 2.
Lademirsen treated population	Randomized population who actually received at least 1 or partial dose of lademirsen during the study

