4.2 PARTICIPANT DISPOSITION

For participant study status, the total number of participants in each of the following categories will be presented using a summary table:

- Nonrandomized but treated participants
- Randomized participants
- Randomized but not treated participants
- Randomized and treated participants
 - Participants who completed the double-blinded, placebo-controlled study treatment period as per protocol
 - Participants who are ongoing the double-blinded, placebo-controlled study treatment period as per protocol
 - Participants who did not complete (eg, treatment early discontinuation) the double-blinded, placebo-controlled study treatment period as per protocol
 - Reasons for treatment discontinuation during the double-blinded, placebo-controlled study treatment period
 - Specified reason for treatment withdrawal by participant during the double-blinded, placebo-controlled study treatment period
 - Participants who completed the open-label extension study treatment period as per protocol
 - Participants who are ongoing the open-label extension study treatment period as per protocol
 - Participants who did not complete (eg, early treatment discontinuation) the open-label extension study treatment period as per protocol
 - Reasons for treatment discontinuation during the open-label extension study treatment period
 - Specified reason with treatment withdrawal by participant during the open-label extension study treatment period
 - Participants who completed the study
 - Participants who withdraw from study
 - Participants who withdraw from study by main reason of study discontinuation
 - Status at last study contact

For all categories of participants (except for nonrandomized categories) percentage will be calculated using the number of randomized participants as the denominator. Reasons for treatment discontinuation will be also provided.

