3 DESCRIPTION OF CHANGES

This SAP Version 2.0 addendum is developed prior to the final DBL (planned for 04 Nov 2022) by following decision to not start Stage 2 enrollment and study termination based on futility analysis result. As the study was terminated early, prior to all Stage 1 participants' completion of the double blind (DB) period of the study, and no Stage 2 participants are enrolled, only key endpoints are planned to be analyzed and the time frame of analysis is reduced to Week 48 for efficacy and most of the safety analyses. Only for limited key safety analyses, the analyses will include up to 96 weeks of the lademirsen treated period. No multiplicity adjustment will be performed. The modified objectives and endpoints are specified in Table 1, which is aligned with the endpoints defined in Amended Protocols 11, 12 and 13. However, there is no major change of the analysis plan regarding the statistical method. For efficacy analyses, as no Stage 2 participants are enrolled, all statistical method will only include Stage 1 participants, and the covariates only pertinent to Stage 2 participants will be removed.

Table 1 - Objectives and endpoints for final analysis (modified after the decision of study termination)

Population ^a	Objectives	Endpoints
Primary		
Primary population	To assess the efficacy of lademirsen in reducing the rate of decline in kidney function as compared to placebo in participants at risk for rapidly progressive Alport syndrome	Annualized rate of change in estimated glomerular filtration rate (eGFR) during the placebo-controlled treatment period
Secondary		
ITT population	To assess the efficacy of lademirsen in reducing the absolute decline in kidney function at Week 48	Absolute and percentage change in eGFR values from baseline at Week 24 and 48 Proportion of participants with a reduction from baseline in eGFR of <10%, <20%, <30%, or <40% at Week 24 and 48
ITT population	To assess the efficacy of lademirsen in delaying time to reach the ESRD	Number and proportion of participants who reach ESRD as defined by an eGFR ≤ 15 mL/min/1.73 m ² or initiation of hemodialysis or renal transplantation (composite endpoint) during the placebo-controlled treatment period

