ITT population	To assess the effect of lademirsen on urine and blood biomarkers in Alport Syndrome participants.	Changes in exploratory biomarkers from baseline at Weeks 24 and 48 during the placebo-controlled treatment period: 
 In both blood and urine^b: β-2 microglobulin and connective tissue growth factor (CTGF) In urine only^b: kidney injury molecule-1 (KIM-1)/creatinine ratio and calbindin-D28k/creatinine ratio
ITT population	To assess the efficacy of lademirsen in reducing the decline in hearing sensitivities at Week 48.	Change from baseline at Week 48 in degrees of hearing level recorded in both ears measured by a pure tone audiometry in the placebo controlled treatment period

^a The definition of population is in [Table 2](#).

^b Urine biomarkers will be standardized by creatinine before analysis. If the urine parameter is collected through 24-hour urine, then the standardized value will be calculated by the original value divided by 24-hour urine creatinine; else if the urine parameter is collected through instant urine, then the standardized value will be calculated by divided by instant urine creatinine.

^c This is one of the primary objectives for Amended Protocol 11 and 12, and secondary objective for Amended Protocol 13.

Table 2 - Populations for analyses

Population	Description
Randomized population	All randomized participants. Participants will be analyzed according to the study intervention allocated by randomization.
ITT population	All randomized participants. Participants will be analyzed according to the study intervention allocated by randomization.
Compliant ITT population	All randomized participants who received $\geq 80\%$ planned IMP during the double-blinded, placebo-controlled treatment period Participants will be analyzed according to the intervention allocated by randomization.
Primary population	All randomized participants who completed the double-blinded period (the first 48 weeks) or discontinued double-blinded period early. Participants will be analyzed according to the study intervention allocated by randomization.
Compliant primary population	All randomized participants who completed the double-blinded period (the first 48 weeks) or discontinued double-blinded period early, and received $\geq 80\%$ planned study intervention during the double-blinded treatment period Participants will be analyzed according to the study intervention allocated by randomization.

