3.1 NEW ANALYSIS

This new analysis was added to this addendum to align with Amended Protocols 11 and 12 because it is described in the Amended Protocols 11 and 12, however removed in Amended Protocol 13.

3.1.1 Proportion of participants with a reduction from baseline in eGFR of <10%, <20%, <30%, or <40% at Weeks 24 and 48

The number and proportion of participants with a reduction from baseline in eGFR of <10%, <20%, <30%, or <40% from baseline at Weeks 24 and 48, respectively, will be summarized by treatment group. In this analysis, since by the time of final analysis, all ITT participants would have had chance to complete Week 24, but some of them may not have chance to reach Week 48 yet, those participants who do not have chance to reach Week 48 will not be included in the denominator for the reduction from baseline at Week 48. Among participants included in the denominator, if any assessments performed at Week 24 or 48, respectively, regardless of scheduled or unscheduled visit, meeting the responder criteria, then the participant will be considered as a responder; otherwise this participant will be considered as a non-responder (including participants missed the assessment at this specified week). The nominal p-value between treatment groups will be calculated by Cochran-Mantel-Haenszel method (CMH) method adjusting for screening eGFR stratification factor.

Signature Page for VV-CLIN-0636754 v1.0
act16248-16-1-9-sap-addendum

Approve & eSign

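### The addendum moves the primary eGFR slope from ITT to a set of participants who completed or discontinued early, and does not say where participants stopped by the termination belong

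*SAP*

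**What the plan says.** Protocol Section 7.2.2 states: "The ITT Population will be the primary efficacy analysis population". Section 7.2.5 defines the primary estimand as the difference in mean eGFR slope from baseline to Week 48 in that population, "regardless of whether or not subjects completed the study period of 48 weeks". By the addendum's own account (Section 1), Amendment 11, with Amendment 12 for France, is the latest globally approved protocol.

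SAP v2.0, written for the two-stage design, introduced a Primary population in Table 5: "All randomized participants from Stage 1/Cohort 1 and Stage 2/Cohort 2 excluding subjects with low baseline eGFR". That is a baseline restriction with no condition on completion.

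The addendum keeps the name and changes the content. Its Table 2 defines the Primary population as "All randomized participants who completed the double-blinded period (the first 48 weeks) or discontinued double-blinded period early". Its Table 1 uses this set for the primary slope only. The eGFR change, eGFR-reduction, ESRD, biomarker and hearing endpoints are all on ITT. Section 3 of the addendum says that the study ended before all Stage 1 participants had completed the double-blind period, and that "there is no major change of the analysis plan regarding the statistical method". Section 3.1.1 says of the ITT participants that "some of them may not have chance to reach Week 48 yet".

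**The concern.** The set used for the primary endpoint now depends on status after randomisation, and its definition names only two states. SAP Section 4.2 recognises a third, listed apart from completing and not completing: "Participants who are ongoing the double-blinded, placebo-controlled study treatment period as per protocol". The addendum does not say into which of its two states a participant falls who was still on blinded treatment when the sponsor stopped the study.

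Two programmers could therefore build different primary datasets from the same text. On the narrower reading, three things follow:

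- The slope no longer estimates the approved ITT quantity.
- It discards eGFR values that have been collected and that the model can use.
- It covers different participants from most of the secondary efficacy results in the same table.

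The addendum gives no reason for the narrower set.

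**Working it through.** The documents give no figure to reproduce. The planned power comes from simulations whose SDs are redacted. The check has three parts: the two readings, how many participants they could concern, and what leaving them out would cost.

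**The two readings.** Protocol Section 3.3.1 says: "A discontinuation of study drug occurs when an enrolled subject ceases study drug, regardless of the circumstances, prior to completion of the study". If that is carried over to the double-blind period, everyone either completed or discontinued, and the Primary population equals ITT. Against this, Section 3.3.1 concerns study drug, the addendum does not cite it, and SAP Section 4.2 keeps a separate ongoing state. Table 2 also defines separate compliant versions of the ITT and Primary sets, which would coincide if their parent sets did. The text leaves both readings open.

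**How many participants.** Inputs from the documents:

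- Stage 1 has 43 participants randomised 2:1, with randomisation complete by the end of December 2021 (SAP Section 1.1).
- The final lock was planned for 4 November 2022 (addendum Section 3).
- All ITT participants would have had the chance to complete Week 24 (addendum Section 3.1.1).

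Taking 31 December 2021 as the last randomisation, that participant reaches Week 24 on 17 June 2022 and Week 48 on 2 December 2022, four weeks after the planned lock. The actual stop date is not given. 17 June is the earliest date consistent with Section 3.1.1, and 4 November is the latest useful date. 9 September is a date between them.

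With uniform accrual,

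number short of Week 48 = 43 × (days from [stop date − 48 weeks] to 31 December 2021) / (accrual length in days).

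The numerator days are 168, 84 and 28 for the three stop dates. For 17 June and 52 weeks of accrual, this gives 43 × 168/364 = 19.8.

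Three accrual lengths were used:

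- **52 weeks** is the SAP's planning assumption (Section 2).
- **72 weeks** assumes that 24 participants had reached Week 48 by the first lock on 22 April 2022. Those 24 were randomised by 21 May 2021, leaving 43 − 24 = 19 in the remaining 32 weeks, so 43/19 × 32 ≈ 72 weeks. The 24 is an interim trigger in the protocol's amendment history and serves here only as an assumption.
- **104 weeks** is a longer alternative.

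**Cost in precision.** For participant i with visit times t, let Z = [1, t], X = [Z, treatment × Z] and V = Z G Z′ + σ²I. The variance of the slope difference is the treatment-by-time element of (Σ X′V⁻¹X)⁻¹. The SE ratio compares the sum over participants with at least 48 weeks of potential follow-up with the sum over all 43. Visits are at Weeks 0, 2, 4 and every four weeks to Week 48. Because the SDs are redacted, the assumed values are intercept SD 10 or 20, slope SD 4 to 8 and residual SD 3 to 6.

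| Accrual | Stop date | Excluded of 43 | SE ratio | Information lost |
|---|---|---|---|---|
| 52 weeks | 17 Jun | 20 | 1.21–1.32 | 31–42% |
| 52 weeks | 9 Sep | 10 | 1.10–1.13 | 18–22% |
| 52 weeks | 4 Nov | 3 | 1.03–1.04 | 6–7% |
| 72 weeks | 17 Jun | 14 | 1.12–1.19 | 20–29% |
| 72 weeks | 9 Sep | 7 | 1.07–1.09 | 12–15% |
| 72 weeks | 4 Nov | 2 | 1.02–1.03 | 4–5% |
| 104 weeks | 17 Jun | 10 | 1.08–1.12 | 14–20% |
| 104 weeks | 9 Sep | 5 | 1.05–1.06 | 9–11% |
| 104 weeks | 4 Nov | 2 | 1.02 | 4–5% |

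**Selection.** Among recently randomised participants the narrow set keeps those who dropped out and removes those who stayed. I assumed 10% drop-out a year, as in the SAP's planning, and a drop-out hazard multiplied by exp(0.5) or exp(1.0) for each SD of faster decline. The mean slope in the retained set then shifts as follows, in mL/min/1.73 m²/year:

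- 72-week accrual, 4 November stop: −0.01 to −0.04
- 72-week accrual, 17 June stop: −0.06 to −0.23
- 52-week accrual, 17 June stop: −0.11 to −0.38

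The target difference is 5. A shift that is equal in both arms cancels from the treatment comparison.

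**The case against.** The best answer is that the natural reading costs nothing. Once the sponsor has ended the study, a participant either finished 48 weeks or stopped before then, and Protocol Section 3.3.1 counts any cessation of study drug as discontinuation. SAP Section 5.3 includes all collected data whether or not the treatment period was completed. The ongoing row in SAP Section 4.2 can be explained as a reporting category for a plan with several interim analyses. Table 2 already contains one redundant pair, because the Randomized and ITT populations have identical definitions; redundancy is therefore weak evidence that Primary and ITT differ.

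The upper end of the size is also stretched. The June stop is only the earliest possible date, and 52-week accrual gives about 17 participants at Week 48 by the first lock, against the 24 assumed for the middle case. The counts are taken before removing drop-outs, who would stay in the set, so they run slightly high. Finally, the study had already been stopped for futility.

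Much of this stands. The effect may be zero, the largest figures are bounds, and the programme decision is unlikely to change. None of it settles which reading applies. The rule on using all data governs which values count for people in the set, and does not decide who belongs to it. Addendum Section 3.1.1 itself treats participants with no chance to reach Week 48 differently from those who merely missed the assessment, so the authors knew of this group and left it unclassified for the primary endpoint.

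**Conclusion.** The point holds and should be fixed. The addendum replaces ITT with a set defined after randomisation for the primary endpoint alone, and leaves open whether participants stopped by the termination are in it. If termination counts as early discontinuation, the effect is zero. Otherwise the middle accrual case excludes 2 to 14 of 43 participants and raises the standard error by 2% to 19%; the outer bounds are 2 to 20 participants and 2% to 32%. These sizes rest on assumed stop dates, accrual and SDs.

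The harm is lost precision and departure from the approved estimand. Bias in the treatment difference is a small secondary risk, since it needs the link between drop-out and slope to differ by arm. Nothing suggests that the redefinition favours lademirsen.

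**What to change.** In addendum Table 1, assign the primary slope to the ITT population, using all double-blind eGFR values up to Week 48 or study end, and treat the termination as administrative censoring. In Table 2, state whether termination counts as discontinuing the double-blind period early, and report the number of participants affected in each arm. Keep the present Primary population as a sensitivity analysis; if termination does count, it will simply reproduce the main result.

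The cost is one table cell and one sentence. The data are already collected and the model is unchanged.
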